| INTERVENTIONS | 
Participants will be randomized to one of three treatments:
 
 • Cognitive Behavioral Therapy (CBT) • Mindfulness-Based Stress Reduction (MBSR) • Usual medical care |
| INTERVENTION SCHEDULE | 8 weekly classes of CBT or MBSR plus daily home practice |
| SAMPLE SIZE | 297 participants (99 CBT, 99 MBSR, 99 usual care) |
| RECRUITMENT PERIOD | Participants will be recruited in 9 cohorts of 33 persons each over a 24-month recruitment period |
| STUDY AIMS | 1) To determine whether Mindfulness-Based Stress Reduction (MBSR) is an effective adjunct to usual medical care for persons with chronic back pain. |

2) To compare the effectiveness of MBSR and group Cognitive-Behavioral Therapy (CBT) in decreasing back pain-related functional limitations and pain bothersomeness.

3) To identify the mediators of any observed effects of MBSR and group CBT on pain-related functional limitations and pain bothersomeness.

4) To compare the cost-effectiveness of MBSR and group CBT as adjuncts to usual care for persons with chronic back pain.

**Co-PRIMARY TRIAL
OUTCOMES**

1) Modified Roland-Morris Disability Questionnaire (back-related dysfunction). This is the most important outcome and was used to calculate statistical power for Aims 1 and 2.

2) Bothersomeness of low back pain (0 to 10 scale).

These outcomes will be measured at baseline, at 4 weeks (during classes), 8 weeks (at the end of classes), 26, and 52 weeks. The 26 week outcomes will be used as the primary endpoint and all other time-points will be considered secondary evaluations.

SAFETY OUTCOMES

Any adverse events identified during classes, on the follow-up interviews or through other means will be documented and reported on a regular basis to the Data Safety Monitoring Body (DSMB). Serious adverse experiences will be reported to the DSMB within 7 days. If attributable to the interventions, serious adverse experiences will also be reported to the IRB within 7 days.

**POTENTIAL MEDIATING
VARIABLES**

We hypothesize: 1) that any benefits of MBSR on participant function and pain bothersomeness will be mediated through increased participant mindfulness and acceptance of pain, and 2) that any benefits of CBT will be mediated through changes in specific cognitions and coping behaviors, as listed in the Specific Aims. We will assess each potential mediator in each follow-up interview.

Mediators of MBSR Effects on Outcomes:

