116 ***Hypothesis 2: MBSR will be more effective than group CBT in decreasing pain-related***
117 ***functional limitations and pain bothersomeness in both the short and long term. The***
118 ***rationale for this hypothesis is based on: a) the modest effectiveness of CBT for chronic***
119 ***back pain found in past studies, b) the positive results of the limited initial research***
120 ***evaluating MBSR for chronic back pain, and c) growing evidence that an integral part of***
121 ***MBSR (but not CBT) training, yoga, is effective for chronic back pain.***
122

123 ***Aim 3. To identify the mediators of any observed effects of MBSR and group CBT***
124 ***on pain-related functional limitations and pain bothersomeness.***

125 ***Hypothesis 3a: The effects of MBSR on functional limitations and pain will be mediated***
126 ***by increases in mindfulness and acceptance of pain.***

127 ***Hypothesis 3b: The effects of CBT on functional limitations and pain will be mediated***
128 ***by changes in pain-related cognitions (decreases in catastrophizing and beliefs one is***
129 ***disabled by pain and that pain signals harm, increases in perceived control over pain***
130 ***and self-efficacy for managing pain) and coping behaviors (increased use of relaxation,***
131 ***task persistence, and coping self-statements; decreased use of rest).***
132

133 ***Aim 4. To compare the cost-effectiveness of MBSR and group CBT as adjuncts to***
134 ***usual care for persons with chronic back pain.***

135 ***Hypothesis 4: Both MBSR and group CBT will be cost-effective adjuncts to usual care.***
136

137 We will also explore whether certain patient characteristics predict or moderate
138 treatment effects. For example, we will explore whether patients with higher levels of
139 depression are less likely to improve with both treatments (i.e., depression level is a
140 nonspecific predictor of treatment effects), or whether such patients are more likely to
141 benefit from CBT than from MBSR (i.e., depression level is a moderator of treatment
142 effects).

143 If MBSR and/or group CBT are more effective than usual care alone, and found
144 to be cost-effective, this evidence could help inform policy decisions for chronic back
145 pain care. Because of the high prevalence and costs of this problem, safe and low cost
146 treatments of even modest effectiveness could produce a large benefit on a population

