734 significant, we will go on to test whether there is a difference between MBSR and Usual
735 Care to address Aim 1 and a difference between MBSR and CBT to address Aim 2. We
736 will also report the comparison of CBT to Usual Care. When determining that MBSR is
737 an effective treatment for back-pain we will require that Aim 1, the comparison of MBSR
738 to Usual Care, must be observed.

739 Based on our previous back pain trials, we
740 expect at least 90% follow-up rate and so our primary analysis will be a complete case
741 analysis including all observed follow-up outcomes, but we will adjust for all baseline
742 covariates that are predictive of outcome, probability of being missing, or differences
743 between treatment groups. By adjusting for these baseline covariates our model
744 assumes that the missing outcome data are missing at random instead of missing
745 completely at random. We will also conduct sensitivity analysis using an imputation
746 method for non-ignorable non-response to evaluate whether our results are robust to
747 different missing data assumptions

748 If MBSR or CBT is effective (relative to usual
749 care and/or each other) in improving either primary outcome at 26 or 52 weeks, we will
750 move to Aim 3 (to identify the mediators of the effects of MBSR and group CBT on pain-
751 related functional limitations and pain bothersomeness). We will perform the series of
752 mediation analyses separately for the two primary outcomes (Roland and pain
753 bothersomeness) and for each separate treatment comparator of interest (usual care-
754 CBT, usual care-MBSR, CBT-MBSR). We will conduct separate mediator analyses for
755 the 26-week and 52-week outcomes (if MBSR or CBT is found effective at those
756 timepoints). Below is the detailed description of the mediator analysis for the 26-week
757 time-point, but a similar analysis will be conducted for the 52-week time-point.

758 We will apply the framework of the widely
759 used approach of Baron and Kenny. Having demonstrated the association between the
760 treatment and the outcome variable (the “total effect” of the treatment on the outcome),
761 the second step will be to demonstrate the association between the treatment and each
762 putative mediator. We will construct a regression model for each mediator with the 4 or
763 8-week score of the mediator as the dependent variable and baseline score of the

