764 mediator and treatment indicator as independent variables. We will conduct this for
765 each potential mediator and only include those mediators that have at least a P < 0.10-
766 level significant relationship with the treatment as potential mediators in the following
767 step. The third step is to demonstrate the reduction of the treatment effect on the
768 outcome after removing the effect of the mediator(s). We will construct a multi-mediator
769 inverse probability weighted (IPW) regression model. This approach allows us to
770 estimate the direct effect of treatment after rebalancing the treatment groups with
771 respect to the mediators. The application of the IPW approach, as compared to the
772 traditional approach of adjusting for multiple mediators, allows us to more appropriately
773 account for confounding between a mediator and the outcome both by additional
774 mediators and by other measured variables. Further, we are better able to estimate the
775 indirect effects of each mediator in a causal framework through decomposition of the

776 total effect of treatment into indirect effects through each mediator and the direct effect
777 after accounting for all mediators. Specifically, we will first model the probability of the
778 treatment given the mediators (all mediators that were found associated with treatment
779 in step 2) using logistic regression adjusting for potential baseline confounders. From
780 this model we will obtain the estimated probabilities that each person received their
781 observed treatment given their observed mediator value. We will then use an IPW
782 regression to model the primary outcomes on treatment status while adjusting for the
783 baseline level of the outcome and mediator. Comparing the weighted to the unweighted
784 model will allow us to estimate how much of the direct effect of treatment on the
785 outcome can be explained by each potential mediator. The inclusion in Step 3 of all
786 mediators found to be significant in Step 2 will enable us to examine whether the
787 specific variables we hypothesized to differentially mediate the effects of MBSR versus
788 CBT in fact mediate the effects of each treatment, independently of the effects of the
789 other “process variables”.

790
791 **9.3 Cost Effectiveness Analyses:** A societal perspective cost-utility analysis (CUA) will
792 be performed comparing the incremental societal costs for each treatment arm (direct

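### Aim 3 screens mediators at P < 0.10 separately in each Usual Care comparison, which cannot by itself show whether MBSR and CBT work through different mediators

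*Protocol*

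**What the plan says.** The Protocol Highlights (Potential Mediating Variables) and Hypotheses 3a and 3b in Section 2 give each program its own mediators. For MBSR, "any benefits of MBSR on participant function and pain bothersomeness will be mediated through increased participant mindfulness and acceptance of pain". Hypothesis 3b begins "The effects of CBT on functional limitations and pain will be mediated" and goes on to pain-related cognitions and coping behaviors.

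Section 6.31 expects the two programs to act through different variables, but undertakes to explore the effect of every candidate on outcomes in both treatment groups.

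Section 9.2 sets the procedure. Aim 3 is entered if MBSR or CBT is effective relative to Usual Care or to each other on either primary outcome at 26 or 52 weeks. The analyses are then run separately for the two primary outcomes and "for each separate treatment comparator of interest": Usual Care-CBT, Usual Care-MBSR and CBT-MBSR. The sequence follows Baron and Kenny:

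- Step 1 presupposes that the treatment-outcome association has been shown.
- Step 2 regresses the 4- or 8-week mediator score on treatment and the baseline score, and will "only include those mediators that have at least a P < 0.10" relationship with treatment.
- Step 3 is an inverse-probability-weighted model containing the survivors.

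The section ends by saying that this will allow an examination of whether the "specific variables we hypothesized to differentially mediate the effects of MBSR versus" CBT do mediate the effects of each treatment, independently of the other process variables.

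**The concern.** The closing statement of Section 9.2 invites a comparison between programs, but the procedure that feeds it consists of separate screens. Three things follow.

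- A mediator that misses P < 0.10 in one Usual Care comparison is not carried into step 3 there, so it has no indirect effect for that program, whatever the weighted model would have shown. Section 6.31's undertaking is then not met for that mediator and program.
- The two step-3 models can contain different co-mediators. Independence from the other process variables then means something different in each, and the results cannot be set side by side.
- A pass in one comparison and a fail in the other is not evidence that the programs differ on that mediator.

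At stake is the interpretation of Aim 3. The report could describe different mechanisms when both programs moved the same mediators by the same amount.

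**Working it through.** **The plan's own figure.** Section 9.1 gives 88 evaluable per group for 30% versus 55% with 90% power. Take a two-sided 0.05 test, a mean proportion of 0.425 and a difference of 0.25:

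n = [1.960 × √(2 × 0.425 × 0.575) + 1.282 × √(0.30 × 0.70 + 0.55 × 0.45)]² / 0.25² = (1.370 + 0.867)² / 0.0625 ≈ 80.1, so 81.

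The continuity correction gives (80.1/4) × [1 + √(1 + 4/(80.1 × 0.25))]² ≈ 87.9, so 88. With 11% loss, 264/0.89 = 296.6, so 297. The stated sample size reproduces and fixes the precision of the screen.

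**Inputs for the screen.** From the protocol: 88 per arm, 1:1:1 allocation, threshold P < 0.10. Assumed, because the protocol gives no mediator effect size or SD:

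- a standardized shift d that is the same in MBSR and CBT;
- a baseline to follow-up correlation r of 0 or 0.5;
- a two-sided screen (|z| > 1.645);
- equal variances and no clustering by class cohort.

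**Formula.** Each contrast with Usual Care is a z-statistic with mean d × √(88/2) / √(1 − r²). The two share the Usual Care arm and so correlate 0.5. Let S be the probability that one screen passes and B the probability that both pass (bivariate normal). The probability that exactly one passes is 2(S − B).

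Example with d = 0.2 and r = 0.5: mean z = 0.2 × 6.633 / 0.866 = 1.532; S = 0.456; B = 0.290; 2 × (0.456 − 0.290) = 0.33.

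| d | S, B at r = 0.5 | Exactly one passes | S, B at r = 0 | Exactly one passes |
|---|---|---|---|---|
| 0.2 | 0.456, 0.290 | 33% | 0.377, 0.218 | 32% |
| 0.3 | 0.743, 0.611 | 26% | 0.635, 0.479 | 31% |
| 0.4 | 0.922, 0.867 | 11% | 0.843, 0.748 | 19% |
| 0.5 | 0.986, 0.973 | 2.5% | 0.953, 0.917 | 7% |

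The maximum is about 33%, reached where each screen has about 50% power. A direct MBSR-CBT test at 0.05 would wrongly declare a difference for 5% of such mediators at every d.

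**Across the mediator set.** The schedule in Section 6 lists ten: FFMQ-SF, CPAQ-8, PSEQ, four SOPA scales, PCS and two CPCI scales. Assume all ten are shifted equally by both programs, with mutual correlation 0.4 and r = 0.5. By simulation, the chance of at least one discordant pair of screens is 95%, 86%, 53% and 17% at 0.2, 0.3, 0.4 and 0.5 SD. The like-for-like figure for the direct test at 0.05 is about 32% at every d, and at 0.10 about 54%.

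**Would the direct contrast help?** Under the same assumptions, when the two screens disagree, the direct test at 0.05 is non-significant in about 83-88% of cases for shifts of 0.2 to 0.4 SD. It would usually show that the apparent difference is unsupported.

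**The case against.** The strongest reply is that Section 9.2 contains no rule crediting a mediator to a program. A reader might infer that a mediator passing against Usual Care for MBSR and failing for CBT is thereby assigned to MBSR. The text does not say so: P < 0.10 only admits a variable to step 3, where mediation is judged. Aim 3 itself asks which variables mediate each treatment's effects, and that can be answered within each comparison with Usual Care. This stands, and the point is limited accordingly. What remains is the section's own reference to differential mediation, and the fact that exclusion at the gate is final for that comparison.

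Second, CBT-MBSR is a named comparator, so a direct contrast is planned. A reader might infer either that it is absent or that it settles the matter. Neither is right. The Baron and Kenny sequence presupposes a demonstrated association with outcome, so without an MBSR-CBT outcome difference that series may not run. If it does run, its step 2 serves as a screen. Nor can one say the plan expects no such difference: 55% in each program is a sample-size input, while Hypothesis 2 expects MBSR to do better and Section 9.1 also considers 76% versus 55%.

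Third, it is tempting to set the 95% for any of ten mediators against the 5% for a direct test. Those are unlike quantities; the matching figure is about 32%. At 0.5 SD with r = 0.5, the screens disagree less often (17%) than the direct test errs. Section 9.1's detectable Roland difference, 2.95/6.0 = 0.49 SD, shows that effects of that order are contemplated for outcomes, though it does not fix the mediator shifts.

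Last, Section 6.3 labels the mediators exploratory. That is correct and limits the weight of the point.

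**Conclusion.** The point holds in limited form. Separate P < 0.10 screens against Usual Care do not support statements that a mediator is specific to MBSR or to CBT. They can leave the two step-3 models with different contents, and the planned CBT-MBSR series does not reliably supply the missing contrast.

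The size depends on a mediator effect that the protocol does not give. For equal true shifts of 0.2 to 0.3 SD, roughly a quarter to a third of mediators would pass exactly one screen; at 0.4 SD, 11-19%. At 0.5 SD the figure is 2.5-7%, about the direct test's own 5%, and the problem is no longer material. The any-of-ten figures describe a scenario in which every mediator is shifted equally, not a forecast. Since Aim 3 is exploratory, no efficacy conclusion under Aims 1 or 2 is affected. The change is worth making because it is cheap.

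**What to change.** Amend the mediation text of Section 9.2 in two places.

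1. Carry the same mediator set into step 3 of both Usual Care comparisons, namely every mediator that passes the screen in either one.
2. Rest any statement that a mediator is specific to MBSR or to CBT on the direct MBSR-CBT contrast for that mediator, reported as an estimate with its confidence interval whether or not the outcomes differ between the two arms. State that passing one screen and failing the other is not grounds for such a claim.

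The mediators are already scheduled in all arms, so only wording changes. The cost is a few more variables in the weight models and hence slightly more variable weights. Two limits should be acknowledged. The contrast compares mediator levels and is not a test of differing indirect effects. It also carries its own error across ten mediators (about 32% for at least one false call at 0.05 under the assumptions above), so the intervals should be read as a set.

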3.8. Participant Retention and Adherence

A Research Assistant from the study will monitor class attendance in the 8-week CBT and MBSR classes. Participants will receive a reminder call before the first class and whenever they miss any classes. The investigators will use this information to document adherence with these interventions.

During each class, participants will be reminded of the importance of attending classes and of practicing at home. A portion of each class will be devoted to answering questions that arise during home practice and, if necessary, to exploring any perceived barriers to adherence. To monitor adherence with the home practice assigned by the CBT and MBSR instructors we will also ask participants to record their daily home practice on weekly logs. To facilitate accurate reporting of home practice, a study Research Assistant will collect the home practice logs at the beginning of each class. The logs will not be shown to the class instructors. Questions about practice in the prior week will also be included in all follow-up interviews. To maintain interviewer blinding, adherence questions will be asked only after all outcomes data are recorded.

To optimize response rates on the follow-up assessments, we will send advance letters before the all follow-up interviews reminding participants they will be called and we will also compensate them \$20 for their time in completing each of the follow-up interviews. This approach has worked well in our previous studies of yoga, acupuncture, and massage.

418 There are a variety of conceivable reasons participants may prematurely discontinue
419 the class series and study staff will use the following groupings to categorize them:

- 420 - Practice of CBT or MBSR associated with unacceptable or serious adverse
421 experiences from perspective of participant
- 422 - Continued participation considered inadvisable by investigator, class instructor or
423 participant's physician due to concerns that continued participation poses an
424 unacceptable risk to the patient.
- 425 - Participants do not care for the class environment
- 426 - Interventions perceived as ineffective by participant
- 427 - Events in participant's life unrelated to trial (e.g., illness or death in family)

428 A study withdrawal form will be completed for individual who discontinues the
429 intervention. In all cases, participants who discontinue treatments will be encouraged to
430 complete the remaining follow-up interviews.

431 432 **4. DATA COLLECTION, QUALITY CONTROL AND CONFIDENTIALITY**

433 Data will be collected from participants by trained telephone interviewers at baseline,
434 about midway through the treatment period (4 weeks after randomization), 8 weeks
435 after randomization (just after the classes have ended), and 26 and 52 weeks after
436 randomization. Reminder letters will be sent before each follow-up interview.

437 Interviewers will be blinded to participants' treatment assignments. Interview data will
438 be collected with a computer-assisted telephone interview (CATI) version of the
439 questionnaires to minimize errors and missing data. Questions about experiences with
440 specific aspects of the interventions (e.g., yoga, meditation, instruction in coping
441 strategies) that would unmask interviewers to treatment group will be asked at the end
442 of an interview, after all other outcomes are assessed. We will attempt to obtain
443 outcome data from all participants in the trial, including those who never attend or who
444 drop out of the classes, who discontinue enrollment in the health plan, and who move
445 away. We will send participants \$20 after each interview completed to maximize
446 response rates.

447 We will collect information at every stage of recruitment, randomization, and
448 treatment so we can report patient flow according to the CONSORT guidelines. We will
449 adapt our standard quality control procedures to monitor the trial, verify accuracy of data
450 collection and analyses, and ensure patient confidentiality

451 We will implement procedures to ensure that all data collection processes are
452 proceeding smoothly. These procedures will ensure that randomization is proceeding
453 as planned, recruitment is on schedule, data collection forms are accurately entered into
454 databases, the computerized assisted telephone interviewing (CATI) system is storing
455 data correctly and that data can be accurately transferred and retrieved as needed. We
456 will develop a relational database to track information on every stage of recruitment,
457 randomization, class attendance, and outcomes assessment so we can report patient
458 flow automatically and in an integrated fashion using standard, automated reports. All
459 data system processes will be thoroughly tested prior to the start of recruitment.

460 The computerized interviewing programs will contain range and logic checks.
461 Participant attendance information collected during the classes will be double key
462 entered into a computer database that also contains logic checks. Prior to recruitment,
463 all data systems will be tested with imaginary participants. Data will be examined for

464 completeness using computer programs developed specifically for that purpose. In
465 addition, we will test all analytic programs to ensure that the analyses are accurate.

466 To maintain the confidentiality of patient-related information in the database,
467 unique participant study numbers will be used to identify patient outcomes and
468 treatment data. The password security system will assign appropriate levels of
469 computer privileges to different groups of database users. This will ensure that all
470 masked personnel remain masked to treatment group.

471 Computer files with participant names will be password protected with access
472 restricted to staff using this information to recruit participants, contact class participants
473 or obtain follow-up data, and interact with any patients reporting adverse events. Any
474 paper data forms, such as homework logs, identifiable only by unique study ID
475 numbers, will be kept in locked filing cabinets. Finally, all analysis data files will be
476 password protected. Full data backup procedures are performed nightly, with partial
477 data back-up throughout the day.

478 **5. TRAINING AND MONITORING OF CLASS INSTRUCTORS**

479 MBSR training will be provided by two Masters level psychotherapists. Both have
480 received training from [name] teacher training program at the Center for
481 Mindfulness at the University of Massachusetts, have taught at least 20 MBSR courses,
482 have worked with Group Health patients, and have had a personal meditation practice
483 for over 15 years. Two PhD-level clinical psychologists with previous experience
484 conducting CBT with patients with chronic pain will provide the CBT intervention. Drs.
485 [name] and [name] will thoroughly train the psychologists to conduct the CBT groups.

486 During the class series, Drs. [name], [name] and [name] will be in weekly
487 contact with the instructors and will inquire about positive experiences, adverse events,
488 concerns raised by participants, ability to stay within the protocol, and any other
489 questions that may arise. Research Assistants will attend each of the classes to collect
490 home practice information and take attendance. Treatment fidelity will be monitored in
491 the MBSR classes by [name] and the Research Specialists. [name] will
492 attend the first class of every session and complete the treatment monitoring and fidelity
493 checklist. Subsequent classes will be monitored by Research Specialists trained by Dr.
494 [name]. Treatment fidelity will be monitored in the CBT classes by Drs. [name] and
495 [name] and the Research Specialists. [name] or [name] will attend the first
496 class of every session and complete the treatment monitoring and fidelity checklist.
497 Subsequent classes will be monitored by Research Specialists trained by [name].

498 **6. ASSESSMENT OF OUTCOMES**

499 We will assess a variety of baseline characteristics including sociodemographic
500 characteristics (gender, age, race, ethnicity, education level, employment status, and
501 marital status), back pain history (e.g., years since first episode of back pain, duration of
502 current episode) and other factors that are prognostic of resolution of back pain (e.g.,
503 number of pain sites and patient expectations of treatment outcome). We will ask
504 participants assigned to one of the two mind-body interventions about their expectations
505 of the helpfulness of the mind-body treatments for back pain and the perceived.
506
507

Content of Baseline and Follow-up Questionnaires

SOURCES OF DATA FOR MAP TRIAL

| MEASURES | Base-line Q | 4 wk Q | 8 wk Q | 26 wk Q | 52 wk Q |
|---|--|---------------|--------|---------|---------|
| BASELINE CHARACTERISTICS | | | | | |
| Patient characteristics (education, race, ethnicity, marital status, income, work status, # of pain sites) (age, gender from EMR) | x | | | | |
| Back pain (pain duration, interference with activities, days of pain in past 6 months, previous spinal injections, radiates below knee) | x | | | | |
| Expectations for back pain improvement: 1) in general, 2) as result of mind-body program | x | | | | |
| PRIMARY OUTCOMES | | | | | |
| Back pain-related dysfunction (modified Roland scale) | x | x | x | x | x |
| Bothersomeness of back pain (0-10 scale) | x | x | x | x | x |
| SECONDARY OUTCOMES | | | | | |
| Characteristic pain intensity (GCPS) (average: pain now, worst pain, average pain) | x | | x | x | x |
| Depression (PHQ-8) | x | | x | x | x |
| Anxiety (GAD-2) | x | | x | x | x |
| LBP-related medications used in past week | x | | x | x | x |
| Exercise in past week (LBP-specific and general) | x | | x | x | x |
| Global improvement (PGIC) | | | x | x | x |
| Program's impact on thoughts, feelings, reactions, activities (open ended) | | | x | x | x |
| EXPLORATORY OUTCOMES: POTENTIAL MEDIATORS | | | | | |
| MBSR: Mindfulness (FFMQ-SF), Pain Acceptance (CPAQ-8) | x | x | x | x | x |
| CBT: Pain beliefs/appraisals (PSEQ; SOPA 2-item Control, Disability, Harm, Emotion scales; PCS), Pain coping strategies (CPCI 2-item relaxation scale, Activity Pacing scale) | x | x | x | x | x |
| EXPLORATORY OUTCOMES: COST-EFFECTIVENESS ANALYSES | | | | | |
| Quality of life (EQ-5D, SF-6D from the SF-12) | x | x | x | x | x |
| Out of plan visits paid for by patients since previous follow-up interview | x | | x | x | x |
| Absenteeism, Presenteeism (WPAI-CLBP) | x | | x | x | x |
| Costs paid by Group Health (payer) for back-related utilization of services (visits, tests, Rx) and total costs. | From electronic medical records for year prior to trial and for follow-up year. | | | | |
| INTERVENTION-RELATED INFORMATION | | | | | |
| Class attendance | | Class Records | | | |
| Adverse experiences from classes or home practice | | X | X | X | X |
| New serious health problems since entering study? | | X | X | X | X |
| Self-reported home practice | | X | X | X | X |
| Perceived helpfulness of classes/home practice | | | X | X | X |
| Would recommend program to friends | | | X | X | X |

510 **Abbreviations:** CPAQ=Chronic Pain Acceptance Questionnaire; CPCI=Chronic Pain Coping Inventory; EQ-5D=European
511 Quality of Life Instrument; FFMQ=Five-Facet Mindfulness Questionnaire; GAD=Generalized Anxiety Disorder scale;
512 GCPS=Graded Chronic Pain Scale; PCS=Pain Catastrophizing Scale; PGIC=Patient Global Impression of Change; PHQ=Patient
513 Health Questionnaire; PSEQ=Patient Self-Efficacy Questionnaire; SF-12=Medical Outcomes Study, Short-Form 12;
514 SOPA=Survey of Pain Attitudes; WPAI-CLBP=Work Productivity and Activity Impairment Questionnaire-Chronic Low Back
515 Pain.

516
517 We will measure a core set of recommended outcomes for spinal disorders (back-
518 related function, pain, general health status, work disability and patient satisfaction) that
519 are consistent with the IMMPACT recommendations for clinical trials of chronic pain
520 treatment efficacy and effectiveness. We will measure outcomes after completion of the
521 interventions (8 weeks) and again after 26 and 52 weeks to determine if any short-term
522 benefits persisted or increased and if participants continued to practice their new skills.

523 In addition, a brief 4-week mid-treatment assessment will focus on collecting data for
524 the analyses of the hypothesized mediators of the effects of MBSR and CBT on the
525 primary outcomes. The primary study endpoint is 26 weeks.

526 527 528 529 6.1 Co-Primary Outcome Measures

530 *Back-related dysfunction* will be measured with the modified Roland Disability
531 Questionnaire ("Roland scale") which asks whether 23 specific activities were limited
532 due to back pain during the past week (yes or no). This measure has been found to be
533 reliable, valid and sensitive to clinical changes, and is appropriate for telephone
534 administration and patients with moderate disability.

535 *Symptom bothersomeness* will be measured by asking participants to rate how
536 "bothersome" their back pain has been during the previous week on a 0 to 10 scale (0 =
537 "not at all bothersome" and 10 = "extremely bothersome"). This question worked well in
538 our previous trials and is highly correlated with a 0-10 measure of pain intensity (r=0.8
539 to 0.9). It is also highly correlated with measures of function and other outcome
540 measures. The validity of numerical rating scales of pain has been well documented,
541 and such scales have demonstrated sensitivity to detecting change in pain after
542 treatment.

543 We will analyze and report these co-primary outcomes in two ways. First, for our
544 primary endpoint analyses, we will compare the percentages of participants in the three
545 treatment groups who achieve clinically meaningful improvement (at least 30%
546 improvement from baseline) in each time point with 26-week follow-up the primary time
547 point. We will then examine, as a secondary outcome analysis, the adjusted mean
548 differences between groups on these measures at follow-up.

549 550 6.2 Secondary Outcomes:

551 *Depression* will be assessed with the Patient Health Questionnaire-8 (PHQ-8) which
552 measures both depression severity and current DSM-IV depression diagnostic status.
553 With the exception of the elimination of a question about suicidal ideation, the PHQ-8 is
554 identical to the PHQ-9, which has been found reliable, valid, and responsive to change.

555 *Anxiety* will be measured with the 7-item Generalized Anxiety Disorder scale (GAD-
556 7), which has demonstrated good reliability and validity in primary care populations and
557 in the general population.

558 *Pain Interference* with normal daily activities will be measured with 3 items from the
559 Graded Chronic Pain Scale (GCPS). The GCPS has been validated and shown to have
560 good psychometric properties in a large population survey and in large samples of
561 primary care patients with pain. We will use the three items that ask participants to rate,
562 on 0 - 10 scales, their degree of pain interference with daily activities, work/housework
563 activities, and recreational/social activities in the past week. The mean of these three
564 ratings has good internal consistency (.89), test-retest reliability (.85 over a 1-2 week
565 interval), and validity, as evidenced by associations with other measures of pain severity
566 and disability.

567 *Global improvement with treatment* will be measured with the Patient Global
568 Impression of Change scale. This single question asks participants to rate their

569 improvement with treatment on a 7-point scale that ranges from “very much improved”
570 to “very much worse,” with “no change” as the mid-point. Global ratings of improvement
571 with treatment provide a measure of the overall clinical benefit from the treatment and
572 are considered one of the core outcome domains for pain clinical trials.

573 *Use of back-related medications and exercise* in past week will be measured on the
574 8, 26 and 52-week questionnaires to provide an indication of how these behaviors were
575 affected by the interventions. They also provide an indication of “co-interventions” that
576 occurred during the follow-up period.

577 *General health status* will be measured with the SF- 12, a widely used instrument
578 that yields summary scores for physical and mental health status. The SF-12 will also
579 be used to calculate quality-adjusted life-years (QALYs) using the SF-6D in the cost-
580 effectiveness analyses.

581 *Qualitative outcomes:* Inclusion of open-ended questions in our previous trials has
582 yielded valuable insights into participants’ feelings about the value of specific
583 components of the interventions and the impact of the interventions on their lives. We
584 will, therefore, include open-ended questions asking about these issues at the end of
585 the 8, 26 and 52-week follow-up interviews.

586 587 **6.3 Exploratory Outcomes**

588 *6.31 Potential Mediators:* For MBSR, we will evaluate the mediating effects of
589 increased mindfulness (measured by the Five Facet Mindfulness Questionnaire) and
590 pain acceptance (measured by the Chronic Pain Acceptance Questionnaire) on the
591 primary outcomes of. For CBT we will evaluate the mediating effects of improvements
592 in pain beliefs/appraisals (measured by the Patient Self-Efficacy Questionnaire; the
593 Survey of Pain Attitudes Control, Disability , Harm, and Emotion Scales; and the Pain
594 Catastrophizing Scale) and improvements in pain coping strategies (measured by the
595 Chronic Pain Coping Inventory’s Relaxation and Activity Pacing scales). Although we
596 expect the effects of MBSR and CBT on outcomes to be mediated by different
597 variables, we will explore the effects of all potential mediators on outcomes for both
598 treatment groups.

599 *6.32. Cost and Effectiveness (Utility) Measures.* Costs will be estimated using cost
600 data from the electronic medical records for back-related services provided or paid by
601 Group Health. The effectiveness of the intervention will be derived from the SF-12
602 general health status measure.

603 604 605 **7. ASSESSMENT OF SAFETY**

606 **7.1 Adverse Events**

607 We will collect data on adverse experiences from several sources and incorporate
608 them into a database. These sources are: 1) reports from the CBT and MBSR
609 instructors of any extraordinary occurrences of concern to them, 2) the computer-
610 assisted telephone-administered 4 and 8, 26 and 52-week follow-up questionnaires
611 will inquire about: any harm they felt from the CBT or MBSR treatments, and any
612 serious health problems, and 3) participants themselves because the consent form
613 directs participants with injuries they believe may be related to the mind-body
614 programs to call the Principal Investigator, Co-Investigators or the Human Subjects

615 Representative, whose names and phone numbers are listed on the copy of the
 616 consent form retained by the participant. Adverse experience data from the
 617 questionnaires will be provided to the Project Manager within a week (and will be
 618 transferred to the AE database). These will be reviewed, as will AE reports from all
 619 sources, by [name], with the assistance of Co-Investigator [name] (a
 620 psychologist) and GHRI physician [name] (a primary care internist) on a
